3.1.1 Monotherapy Dose Escalation (Part 1)

In Part 1 (dose escalation), BMS-986158 is administered as monotherapy (Schedules A, B and C). The study design schematics are presented in Figure 3.1-1 and Figure 3.1-2.

To minimize risks to subjects from unanticipated acute toxicities, a waiting period of at least 5 days will occur between administrations of the first dose for the first, second, and third subjects to create an observation period prior to subsequent subject exposures. This waiting period is mandatory only in the first Cohort of Schedule A of Part 1.

Part 1: Selection of Doses

In Schedule A of Part 1, the first cohort of subjects received a starting dose of 0.75 mg. In this schedule, each subject was administered a single dose of BMS-986158 on Cycle 1 Day 1 (4-to 7-day cycle) and no additional doses were administered until Cycle 2 Day 1. On Cycle 2 Day 1, which must be within 7 days of the Cycle 1 Day 1 dose administration, and on each subsequent cycle, subjects received QD dosing for 5 consecutive days of each week, followed by a 2-day rest period, on a 28-day cycle. The second cohort of subjects on this schedule received a dose of 1.25 mg. This dose level (a 67% increase) was chosen instead of 1.5 mg dose level (a 100% increase) because of the longer than expected half-life that was calculated based on human exposure data from the first cohort of (n=5) subjects evaluated at the 0.75 mg dose level.

For Schedule B, each subject is administered a single dose of BMS-986158 on Cycle 1 Day 1 (7-day cycle) and no additional doses are administered until Cycle 2 Day 1. On Cycle 2 Day 1, and on each subsequent cycle, subjects receive QD dosing for 14 consecutive days, followed by a 7-day rest period, on a 21-day cycle. For Schedule C, subjects are administered a single dose of BMS-986158 on Cycle 1 Day 1 (7-day cycle) and no additional doses are administered until Cycle 2 Day 1. A schedule of 7 days on, 14 days off may be implemented beginning with Cycle 2 Day 1 and on each subsequent cycle, if agreed upon by the Sponsor/Medical Monitor and investigators. Refer to Figure 3.1-2 and Section 4. Subjects enrolled previously in Part 1 who are still receiving

therapy will continue to be dosed on their original schedule. Subjects may continue to receive treatment until disease progression, unacceptable AEs or withdrawal of consent, or as defined in Section 3.5.

[figure not shown]
Dose escalation for each subsequent cohort of subjects in each of the schedules will be guided by the incidence of AEs for which no clear alternative cause is identified as graded by National Cancer Institute Common Terminology Criteria for Adverse Events version 4.03 (NCI CTCAE v4.03) in the first 32-35 days of dosing for Schedule A of Part 1. Dose escalation will be in increments of 100% above the previous dose level until the first occurrence of any of the following toxicities that have no alternate cause: any DLT (as described in Section 4.5.1), any \geq Grade 2 toxicities with the following exceptions: Grade 2 fatigue, Grade 2 alopecia.

Once one or more of the above identified DLTs occurs, a modified Fibonacci dose escalation schema will be employed for any subsequent dose escalations at that schedule, with increments of 67%, 50%, 40%, and 33%. Any further dose escalations will be 33%. In addition, dose modification could also include changes in the dosing interval (e.g. twice weekly) based on available safety and PK data.

Intermediate doses may be evaluated if agreed upon by the Sponsor/Medical Monitor and investigators. The next dose level will not exceed 100% or the dose increment per the modified Fibonacci dose escalation schema.

Figure 3.1.1-1: Dose Escalation Decision Scheme

*Complete set of Decision Rules are shown in Appendix 1.

Revised Protocol No.: 07 Date: 18-Mar-2019 Enrollment in dose escalation and selection of the MTD will adhere to a mTPI design. The design provides a simple algorithm for decisions on escalation, expanding at the same dose, and de-escalation, depending on the number of observed toxicities after each dose cohort (see Figure 3.1.1-1). The mTPI method utilizes a target toxicity (DLT) rate and equivalence interval to guide decisions on escalation after each cohort and to estimate the MTD. For this study, the target DLT rate is 27% and the EI is 25%-29%.

Dose escalation decisions will be guided by the cumulative number of subjects who are DLT evaluable and who experience a DLT in the DLT Evaluation Period for all arms (Figure 3.1.1-1 and Appendix 1). If no DLTs are observed in the first dose cohort of Part 1, 3-4 subjects will be enrolled at the next higher dose level. If 1 DLT is observed in 3 or 4 evaluable subjects, this dose level will be expanded by enrolling another cohort of 3-4 at the same dose level. If 2 of 3 or 3 of 4 subjects are observed with DLTs, the next cohort will be enrolled at the next lower dose level. Additional decisions are shown in Figure 3.1.1-1 and Appendix 1. If a decision to treat more subjects at a given dose level is suggested by the mTPI algorithm when there are already at least 13 DLT evaluable subjects treated at the same dose level, a need for further enrollment in the dose escalation phase will be determined by the Sponsor. These same rules will be applied to Schedules B and C. A total of approximately 30 DLT evaluable subjects is expected to be treated per schedule with a total of 90 planned across schedules for the dose escalation phase.

Decisions to escalate, add more subjects to the current dose, de-escalate (with options to re-escalate), or de-escalate and declare the current dose as unacceptable (exceeding the MTD), will be based on the rate of DLTs in evaluable subjects within the 32-35-day DLT evaluation period of Schedule A for Part 1, and within the 35-day DLT evaluation period of Schedules B and C for Part 1 (Appendix 1). At least 3 DLT-evaluated subjects treated at each dose level are required to enable a decision. To account for subjects who may not be able to complete the DLT evaluation period, for reasons other than a DLT, or may not be evaluable for DLT, a fourth subject may be enrolled at this dose level, following agreement between the investigator and Sponsor/Medical Monitor.

DLT-evaluable subjects are defined as subjects who received at least 16 of 21 doses of BMS-986158 in Schedule A of Part 1; at least 17 of 22 doses of BMS-986158 in Schedule B of Part 1; and at least 12 of 15 doses in Schedule C of Part 1 during the DLT evaluation period and will be considered for dose escalation decisions. Subjects who developed a DLT during the DLT period are considered evaluable regardless of the number of received doses. Subjects with insufficient data to establish safety during the DLT evaluation period at the dose level tested may be replaced upon agreement of the Sponsor/Medical Monitor and investigators.

There will be no intrasubject dose escalation of BMS-986158.

Figure 3.1.1-1 shows examples of scenarios guiding decisions that may be encountered during dose escalation with respect to the number of DLT evaluable subjects and the number of subjects with a DLT. All potential combinations of the number of subjects with DLTs and number of treated subjects evaluable for DLT are shown in Protocol Appendix 1. In addition to escalation or expansion decisions, dose re-escalation is permitted as per Figure 3.1.1-1 and Appendix 1 after a

decision to de-escalate is made, except when a dose level has been identified as exceeding the MTD. Therefore, a dose level could be revisited multiple times under the mTPI design.

In addition to the guide for escalation decisions, to better assess if a dose level is safe given the number of DLTs observed, posterior probabilities of the DLT rate are provided in Section 8.1 to inform decisions regarding dose safety.

Part 1: MTD Determination

At the end of dose escalation, the MTD for each evaluated dosing schedule (Schedules A, B, and C) will be selected as the dose with the smaller difference between estimated toxicity and the target DLT rate (27%), among the dose levels used, with an isotonic regression model of the accumulated DLT data based on the mTPI design (Appendix 1).

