APPENDIX 2 SIMULATION OF MTPI VS 3 + 3 DOSE ESCALATION DESIGNS WITH 6 DOSE LEVELS

Simulations of mTPI and 3+3 designs, shown below, demonstrate that the mTPI design has a greater chance of selecting the correct MTD than the 3+3 design, and treating fewer subjects at sub-optimal doses.

The mTPI uses a set of decision rules guided by simple Bayesian models and requires a clinically relevant pre-determined target DLT rate and an equivalence interval (EI), within which any dose is considered close to the true maximum tolerated dose (MTD). For this study, the selected target toxicity (DLT) rate is 27% and EI [25%, 29%].

The mTPI design makes decisions using the same two observed numbers as the traditional 3+3 design, the number of DLT evaluable subjects and the number of subjects with DLT. Based on these two numbers, unit probability mass is calculated within each of three regions as stated above, and decision is based on which region has the largest unit probability mass:

- E: escalating to the higher dose if interval (0, 25%) has the largest unit probability mass,
- S: staying at the same dose if interval [25, 29%] has the largest unit probability mass,
- D: de-escalating to the lower dose if interval (29, 100%) has the largest unit probability mass.

At the end of the trial, MTD will be picked, by isotonic regression estimation method, to be the dose whose estimated toxicity rate is closest to the target toxicity rate among all the tried doses.

Simulations were performed to examine the operating characteristics of mTPI and 3 + 3 designs for this study. Escalation decisions based on the mTPI are shown in the protocol. Decisions based on the 3+3 design are shown below:

- E: no subject with DLT out of 3 DLT evaluable subjects initially, or at most 1 subject with DLT out of 6 DLT evaluable subjects after adding 3 more subjects.
- S: 1 subject with DLT out of 3 DLT evaluable subjects initially.
- D: at least 2 subjects with DLT out of 3 DLT evaluable subjects initially, or at least 2 subjects with DLT out of 6 DLT evaluable subjects after adding 3 more subjects at this dose

Settings for simulation:

- 6 dose-toxicity scenarios, each of which with a number of 6 (expected) dose levels
- 1000 trials per scenario
- Target toxicity (Pt) for mTPI design: 27% with Equivalence Interval (EI) = [25, 29%]

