(%)	mTPI	9	26	47	15	3	1	0	26.8		52
Subjects Allocated	3+3		4.9	4.1	2.2	0.6	0.1	0		12.0	
Allocated (n) mTPI 7.9 7.7 2.5 0.					0.3	0	0		18.4		
Note: The true MTD is dose level 2, the second lowest dose level. In this case of one sub-											

Note: The true MTD is dose level 2, the second lowest dose level. In this case of one suboptimal dose level and four over-toxic dose levels mTPI picks the correct MTD almost 20% more often (47% vs. 29% for 3+3). Selection of sub-optimal doses by the mTPI is much less frequent (35% vs. 60% by the 3+3) while over-toxic dose selection is 7% more likely for mTPI than by 3+3.

Scenario 6				D	ose Lev	vel			DLT	Average	2
									Rate	Sample	Stop
		1	4			4	-	6		Size	Prob.
	-1	1	2	3	4	5	6				
True DLT rate			0.27	0.40	0.50	0.55	0.60	0.65			
MTD	3[contact]	1	0	0	0	40		
Selected (%)	mTPI	30	48	19	2	1	0	0	38.7		54
Subjects Allocated	3+3		5.2	2.7	0.7	0.1	0	0		8.7	
(n)	mTPI		9.3	4.0	0.5	0	0	0		13.8	
Note: The true MTD is dose level 1, the lowest dose, which represents an unlikely case when											
only the lowest dose level is considered to be tolerated. mTPI selects the correct MTD more											
often (48% vs. 36% for the 3+3). mTPI picks no dose (dose level -1) at a much lower rate											
(30% vs. 51% for 3+3), but also chooses high dose levels more frequently (22% vs. 12% for											
(50% vs. 51% for 5+5), but also chooses high dose revers more frequently (22% vs. 12% for $3+3)$.											

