Enrollment in Part 1 and selection of the monotherapy MTD will adhere to a modified Toxicity Probability Interval (mTPI) design. The mTPI method utilizes a target toxicity (DLT) rate and equivalence interval (EI) to make decisions on escalation after each cohort and to estimate the MTD. For this study the target DLT rate is 27% and the EI is 25%-29%. During Parts 1, the monotherapy MTD will be selected as the dose levels with the smaller difference between estimated toxicity and the target DLT rate among the dose levels administered based on the mTPI design. See Protocol Appendix 1.

Figure 2.1-1 shows a graphical depiction of the study design, which shows only Part 1 and Part 2 initial expansion as clarified in the scope of this SAP document in the beginning.

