**Figure 2.1-2: Dose Escalation Decision Scheme**

DLT-evaluable subjects are defined as subjects who received at least 16 of 21 doses of BMS-986158 in Schedule A; at least 17 of 22 doses of BMS-986158 in Schedule B ; and at least 12 of 15 doses in Schedule C of Part 1 during the DLT evaluation period and will be considered for dose escalation decisions. Subjects who developed a DLT during the DLT period are considered evaluable regardless of the number of received doses.

At the end of dose escalation, the MTD for one evaluated dosing schedule (Schedules A, B, or C) will be selected as the dose with the smaller difference between estimated toxicity and the target DLT rate (27%), among the dose levels used, with an isotonic regression model of the accumulated DLT data based on the mTPI design.

Treatment in Part 2 can be initiated before Part 1 is completed and when the MTD (or maximum administered dose if no MTD is determined) for Part 1 has been determined. Schedule A (QD dosing for 5 consecutive days of each week, followed by a 2-day rest period, on a 28-day cycle) has been chosen for expansion. This regimen was selected after considering safety, PK [REDACTED] data generated during Part 1. The initial dose level of BMS-986158 selected for Part 2 is 4.5 mg with a loading period of 2 weeks (10 doses or half a cycle) with subsequent dose level of 3.75 mg for the duration of study treatment for each subject.

BMS-986158 will be first evaluated as monotherapy. The Initial Expansion will enroll a maximum of 45 subjects with tumors harboring specific genetic alterations including fusion proteins (NMC, DHL), BRD amplifications (TNBC), MYC amplifications (Non-GC DLBCL) and AR amplification (CRPC).

Adolescent subjects will be treated with a dose and schedule selected from Part 1 (dose escalation) in adult subjects. The safety of this selected BMS-986158 dose will be evaluated in adolescents ( $\geq 12$  to  $< 18$  years of age) as part of the dose expansion phase (Part 2) in subjects with NMC. Initially, 3 to 4 adolescent subjects across different tumor types may be enrolled in the Initial Expansion and monitored for DLT. Based on safety and other available data, the Sponsor may consider decreasing the dose level of BMS-986158 for adolescent subjects.

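### The Part 1 MTD rule does not exclude dose levels declared unacceptable, so it can name as MTD a dose the protocol says exceeds the MTD

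*Protocol*

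**What the plan says.** Protocol 3.1.1 runs Part 1 on an mTPI design in which "the target DLT rate is 27% and the EI is 25%-29"%. One of the decisions open after each cohort is to "de-escalate and declare the current dose as unacceptable (exceeding the MTD"). Appendix 1 marks those cells DU, and its legend calls the dose unacceptably toxic. The only consequence written for Part 1 is that such a level may not be re-escalated to.

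The MTD rule is stated in several places:

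- Protocol 3.1.1, with the same wording in the synopsis: the MTD for each schedule "will be selected as the dose with the smaller difference between estimated toxicity and the target DLT rate (27%), among the dose levels used".
- Protocol Appendix 2: "the dose whose estimated toxicity rate is closest to the target toxicity rate among all the tried doses".
- SAP 2.1, first statement: "among the dose levels administered based on the mTPI design".
- SAP 2.1, after the decision-scheme figure: "among the dose levels used, with an isotonic regression model of the accumulated DLT data".

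The candidates are all levels used, tried or administered. None of these statements mentions DU. Section 3.1.1 points to Appendix 1 for MTD selection, but Appendix 1 holds only the decision table and its legend.

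The Appendix 2 simulation settings add a nominal level -1 for trials in which de-escalation is called from dose level 1. The Scenario 6 note then reports that "mTPI picks no dose (dose level -1) at a much lower rate", 30% against 51% for the 3+3.

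**The concern.** The DU label and the final selection answer the same question, whether a dose is above the MTD, and nothing in the text makes them agree. A dose can be ruled out during escalation and then win the final comparison, because that comparison uses only absolute distance from 27% and treats distances above and below the target alike. If the level beneath has an estimate near zero, a DU level at about 50% can be the closer one.

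The DLTs, MTD and RP2D of monotherapy are in the primary objective (Protocol 1.3.1, SAP 3.1). Section 4.5 enrols Part 2 subjects at or below the MTD, or at an agreed alternative dose. An analyst applying the rule literally could report an MTD that the protocol's own decision table has rejected.

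**Working it through.** **Inputs.** Target 27% and equivalence interval 25%-29% (Protocol 3.1.1); the E/S/D/DU table (Appendix 1); 3 to 13 evaluable subjects per level (Protocol 8.1); cohorts of 3-4 and at most 30 evaluable subjects (Appendix 2).

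**Step 1: reproduce the plan's table.** For x DLTs in n subjects, take the posterior mass in (0, 0.25), [0.25, 0.29] and (0.29, 1), divide each by its interval length, and choose the largest. Assign DU when P(p > 0.27 | data) > 0.95. The prior and the 0.95 cutoff are not stated and are assumptions here. With a Beta(1,1) prior, 135 of 135 printed cells are reproduced. Beta(1,2.7) misses 21. The DU boundaries used below are therefore those of the plan.

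**Step 2: a permitted path in cohorts of 4.**

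| Step | Dose | Cumulative DLTs | Appendix 1 |
|---|---|---|---|
| 1 | lower | 0/4 | E |
| 2 | next | 1/4 | S |
| 3 | next | 3/8 | S |
| 4 | next | 6/12 | DU |
| 5 | lower | 0/8 | E, but the next dose is barred |

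Total: 8 + 12 = 20 subjects.

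**Step 3: apply the MTD rule.** The rates are already in increasing order, so no pooling is needed.

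| Estimate fed to the isotonic fit | Lower dose (0/8) | Next dose (6/12, DU) | Gaps from 27% (points) | Selected |
|---|---|---|---|---|
| Raw rate x/n | 0% | 50% | 27 and 23 | DU dose |
| Beta(1,1) mean (x+1)/(n+2) | 1/10 = 10% | 7/14 = 50% | 17 and 23 | lower dose |
| Beta(1,2.7) mean (x+1)/(n+3.7) | 1/11.7 = 8.5% | 7/15.7 = 44.6% | 18.5 and 17.6 | DU dose |

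The result turns on the estimator, which the documents leave unnamed.

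**Step 4: how many pairs do this.** All Appendix 1 pairs were listed with a lower level at E or S and an upper level at DU, each with at least 3 subjects. The count is of pairs in which the DU level is closer to 27%.

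| Estimate | Up to 13 per level | Up to 15 per level |
|---|---|---|
| Raw rate | 33 | 80 |
| Beta(1,2.7) mean | 27 | 62 |
| Beta(1,1) mean | 0 | 3 |

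With raw rates and at most 13 subjects, the upper-level counts are 5/10, 6/12 and 7/13. For 5/10 and 6/12 the lower estimate must be below 27 - 23 = 4%. For 7/13 (53.8%, gap 26.8) it must be essentially zero.

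**Step 5: frequency by simulation** (10,000 trials per Appendix 2 scenario). Trials that stopped at dose 1 are set aside, because Appendix 2 would report them as level -1. The literal rule names a DU dose in roughly 0.3% to 1.3% of trials with raw rates, up to about 1.5% across the estimators tried, and 0% to 0.2% with Beta(1,1) means. Under an assumed steep curve (1, 2, 5, 45, 60, 70%), repeated runs give about 6% to 7.5% with raw rates and 0% with Beta(1,1). The simulation is not an exact copy of Appendix 2 (average size about 15-27 against the printed 13.8-21.8), so these figures are indicative.

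**Step 6: the no-dose outcome.** Ending the trial with no MTD at any D or DU from dose 1 gives 29% to 30% in Scenario 6, against the printed 30%. That agrees with the level -1 setting described in Appendix 2. Section 3.1.1 has no such outcome, because its rule always returns one of the levels used.

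**The case against.** The strongest reply is that a dose labelled as exceeding the MTD cannot coherently be the MTD, and that Section 3.1.1 says MTD selection follows the mTPI design, so exclusion is implied. That is a sensible reading, but it is not written down. The section and appendix cited for selection contain no such exclusion, and the SAP, which says it supersedes the protocol's statistical considerations, repeats the inclusive wording. The synopsis reference to an MTD or MAD does not help either, since MAD is for the case where no MTD is reached and the written rule always returns a level.

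The reply that the event is rare and estimator-dependent stands. So does the point that the Part 2 dose was not set mechanically: it was agreed by the sponsor and investigators, and Section 4.5 allows an alternative dose.

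Three stronger readings are not supported:

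- A reader might infer that the no-dose results show the Appendix 2 simulations excluded DU levels, or that a DU-only exclusion would reproduce them. Appendix 2 ties level -1 to any de-escalation from dose 1, plain D included. DU at dose 1 accounts for only about 6% of Scenario 6 trials when a D at dose 1 also stops the trial, so a DU-only rule would not give 30%.
- A reader might point to a lowest dose that is both DU and the only level tried, where the literal rule must return it. Section 1.4.4 shows that every schedule had already been tested at more than one dose level by 21-Dec-2018, so that case is past.
- A reader might infer that a DU dose was named MTD in this trial. The observed DLT counts are not in the documents, and nothing in them shows this.

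**Conclusion.** The concern holds as a gap in the written rule. The protocol can declare a level above the MTD and still select it as the MTD, and the SAP does not close the gap. The contradiction follows from the text, and a path allowed by Appendix 1 produces it. The simulated frequencies are low and rest on an assumed estimator, an assumed prior and cutoff for the decision table and, for the higher range, a dose-toxicity curve that is not in the documents. With Beta(1,1) posterior means no E-or-S/DU pair within 13 subjects per level triggers it. The mismatch between the level -1 convention in Appendix 2 and the Section 3.1.1 rule is a second, separate gap. Because the rule serves the primary objective and the correction is only text, it should be made.

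**What to change.** Reconcile the MTD rule with the protocol's DU definition in the synopsis, Protocol 3.1.1, Appendix 2 and SAP 2.1:

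1. Limit the candidates to dose levels used and not declared DU.
2. State that no MTD is declared if no such level remains.
3. Name the estimate that feeds the isotonic fit (raw rate, or posterior mean with its prior).
4. Either carry the level -1 convention for any de-escalation from dose 1 into Section 3.1.1 and the SAP, or remove it from Appendix 2 and rerun those simulations.

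Items 1 to 3 cost a few sentences and need no extra subjects or data. Item 4 is also a text change if the convention is carried over. Removing it means repeating the Appendix 2 simulations.

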3.1.2 Dose Expansion (Part 2)

Treatment in Part 2 can be initiated before Part 1 is completed and when the MTD or maximum administered dose (MAD), if no MTD is reached for Part 1, has been determined. Schedule A (QD dosing for 5 consecutive days of each week, followed by a 2-day rest period, on a 28-day cycle) has been chosen for expansion. This regimen was selected after considering safety, PK

data generated during Part 1 (see Section 1.1.5). The initial dose level of BMS-986158 selected for Part 2 is 4.5 mg with a loading period of 2 weeks (10 doses or half a cycle) with subsequent dose level of 3.75 mg for the duration of study treatment for each subject. Adult and adolescent subjects weighing \geq 40 kg will be administered a flat dose of BMS-986158. Further dose modification at the subject level is permitted below the dose level of 3.75 mg depending on the observed toxicity and tolerability (see guidelines for dose modification in Section 4.5.2).

BMS-986158 will be first evaluated as monotherapy. The Initial Expansion will enroll a maximum of 45 subjects with tumors harboring specific genetic alterations including fusion proteins (NMC, DHL), BRD amplifications (TNBC), MYC amplifications (Non-GC DLBCL) and AR amplification (CRPC).

Depending on the

safety, preliminary efficacy, tolerability,

a Subsequent Expansion will enroll up to 126 subjects with tumor types already evaluated in the Initial Expansion as well additional tumor types within and across groups of specific genetic alterations. Categories of genetic alterations and tumors under consideration for the Subsequent Expansion include fusion proteins (NMC, DHL, ES and BL), BRD amplifications (TNBC, OC and NEPC), MYC amplifications (Non-GC DLBCL, UCS, OC), AR amplification (CRPC) and mutations (RCC, NSCLC and UM). See Figure 3.1-1.

The decision to assign new cohorts of subjects to BMS-986158 plus nivolumab combination therapy will be made upon agreement between the Sponsor/Medical Monitor and investigators

Revised Protocol No.: 07 Date: 18-Mar-2019 after review of available data obtained from both initial and subsequently enrolled monotherapy expansion subjects. If combination therapy of BMS-986158 and nivolumab is pursued, subjects may be enrolled with any of the tumors types listed in Figure 3.1-1. The tumor types enrolled will depend on the activity of BMS-986158 monotherapy within and across biomarker groups. Based on the results of Part 2, including PK

, discussion between Sponsor/Medical Monitor and the investigators, and additional considerations, enrollment may be initiated for other indications not listed in Figure 3.1-1 as long as subjects meet the specified inclusion criteria (see Section 3.3.1). Up to approximately 327 subjects will be treated in the dose-expansion phase (Part 2) of this study

